7.2 Concomitant Medications

For all medications taken during the procedure and after, the medication name, total daily dose, route, frequency of dosing and indication for use will be recorded on the concomitant medication page in the CRF.

7.3 Randomization and Blinding

Study treatment will consist of FDY-5301 (3 dose levels) or placebo.

All subjects who fulfill all study eligibility criteria will be randomized to receive one of the 4 treatments allocated by a computer generated randomization code. Clinical staff will be kept unaware of treatment allocation as placebo and active vials will be identical in appearance.

8 STUDY DRUG MATERIALS AND MANAGEMENT

8.1 Study Drug

FDY-5301 will be provided as single use vials for injection containing 20 mL of drug product at a concentration of 7.2 mg/mL. The active ingredient sodium iodide (NaI), and the following inactive excipients: sodium chloride, and water for injection.

Placebo will be provided as single use 20 mL vials for injection containing sterile saline solution.

The manufacturing batch (or box number) of investigational product (active drug, placebo) will be recorded on each subject's drug administration case report form (CSR).

8.2 Study Drug Packaging and Labeling

FDY-5301 final drug product will be manufactured and packaged by Alcami on behalf of Faraday Pharmaceuticals, Inc. in accordance with GMP.

Supply and Return of Drug

Clinical supplies will be shipped to sites following the completion of study initiation and receipt of Institutional Ethics Approval.

Labels will be in accordance with all applicable local regulations and may include:

- For Investigational Use Only
- Site identification
- Subject Number (blank for insertion)
- Batch (Lot) Number
- Storage conditions
- Expiry Date
- Sponsor's Name

8.3 Study Drug Storage

Clinical trial materials will be securely stored as supplied (20 to 25 °C) and should not be stored frozen. Direct exposure to sunlight and heat should be avoided.

The sponsor reserves the right to inspect the drug storage area before and during the trial.

8.4 Study Drug Preparation

The formulation has no preservative and is intended for single use only; injection solutions should be prepared using aseptic technique and inspected prior to administration. The solution for injection should be a clear, colorless solution with no particulate matter.

A guide will provide detailed instructions for randomization and calculation of dose of drug (or volume of placebo) and preparation of the intravenous injection. Drug administration by bolus injection to the subject must occur at any time between 60 minutes and 5 minutes prior to reperfusion of the coronary artery.

8.5 Administration

FDY-5301 will be administered intravenously by a healthcare professional. Dosage will be administered on a body weight basis, according to treatment assignment and using the subject's body weight determined on the dose administration day. Preparation of the administered dose will be achieved by adjusting the volume of undiluted solution of 7.2 mg/mL FDY-5301

8.6 Study Drug Accountability

Study drug will only be used for purposes of this study. The clinical site staff will be responsible for the study drug accountability, reconciliation and record maintenance in accordance with all applicable regulatory requirements. The amount of drug received from Faraday Pharmaceuticals and the amount administered to subjects will be documented.

Investigational Product Accountability

An investigational product accountability record for the investigational products mandated by the protocol must be kept current and should contain:

- The dates and quantities of investigational product received from Faraday Pharmaceuticals, Inc.
- manufacturing batch or box numbers for product received
- subject's identification (subject number and initials)
- date and quantity of investigational product dispensed (and remaining, if from individual subject drug units)
- the initials of the dispenser
- date and quantity of drug returned to the investigator/pharmacy, if appropriate

At the end of the study, the final investigational product reconciliation statement must be completed and provided to Faraday Pharmaceuticals.

These inventories must be made available for inspection by an authorized Faraday Pharmaceuticals representative or designee and regulatory agency inspectors. The investigator is responsible for the accountability of all used and unused trial supplies.

8.7 Study Drug Handling and Disposal

Only subjects randomized into the study may receive study drug. Authorized and adequately trained staff will administer the study drug.

The Principal Investigator must maintain accurate records demonstrating dates and amount of drug received, to whom it was dispensed and accounts of any drug accidentally or deliberately destroyed. It will be the responsibility of the Sponsor to ensure that adequate samples of all trial doses are retained in accordance with the relevant regulatory guidelines.

At the conclusion of the trial, a final inventory will be performed by the Sponsor Monitor and the Principal Investigator or nominees. If any supplies cannot be accounted for, this should be documented on the drug accountability form together with an explanation of the discrepancy. The originals of the drug accountability and dispensing logs must be sent to the Sponsor. The Principal Investigator will retain copies of these logs on file.

Any remaining drug at the end of the study will be disposed of as per sponsor instructions (e.g. at the site by using approved drug destruction methods).

9 REPLACEMENT OF SUBJECTS

Any subject who signs an informed consent form but is not randomized will be considered a screen failure and be replaced. Any subject who receives investigational treatment that does not undergo PCI will be followed up for safety but replaced.

10 CMR PROTOCOL

MRI determination of MSI, MI size, MI/VV, and Cardiac Function

Cardiac MRI (CMR) will be performed at 72 +/- 24 hours and 3 months post-study drug at the study site.

The 72 hour CMR will include cine, T2W and LGE imaging for function, edema and necrosis respectively. The 3 month CMR will include cine and LGE for function and late scar quantification respectively.

The primary estimate of AAR and hence MSI will be based on CMR imaging of myocardium for edema (secondarily the length of coronary artery occluded will be document at the time of PCI).

Cardiac function will be assessed by CMR and defined in terms of EDV, ESV, FS and EF.

All MRI data will be analyzed at a central core laboratory. Detailed instructions for the conduct and interpretation of the CMR will be available in a separate document, including the parameters to be analyzed.

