3.3 Rationale

Preclinical pharmacology data to date show that FDY-5301 when administered in conjunction with the revascularization of previously ischemic myocardium significantly reduces infarct size, improves myocardial function and coronary perfusion, reduces neutrophil infiltration and down-regulates the inflammatory response in the reperfused myocardial tissue. FDY-5301 may reduce myocardial reperfusion injury in patients with AMI undergoing revascularization, and consequently, reduce infarct size. No clinical trials in AMI patients have yet been conducted with FDY-5301. The anticipated human effective dose based on preclinical data is from 0.5 to 2.0 mg/kg. The study outlined herein is designed to assess the safety, efficacy and PK of FDY-5301 in patients with first STEMI about to undergo PCI.

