5.5.8 Follow-up 3 months (+/- 2 weeks post drug)

- CMR to measure MSI, INF/VV, INF and cardiac function including EDV, ESV, FS and EF
- Recording of any AEs
- Concomitant medications
- 12-lead ECG including rhythm strip to identify persistent arrhythmias
- Blood sample for analysis of biomarkers of remodeling

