11.4.2 Secondary Efficacy Analysis

11.4.2.1 Infarct Size Parameters from CMR

INF/VV, MSI, and INF will be assessed by CMR at 72 ± 24 hours post-study drug and 3 months post-study drug. Summary statistics for the observed values along with changes from baseline will be produced for each treatment group and the overall FDY-5301 group for each parameter. The baseline is defined as the measurement taken at the 72 hour timepoint.

For the changes from baseline for each of these parameters, a single pairwise comparison will be performed to analyze the results between all three FDY-5301 groups (overall) and placebo at both the 3 months post-study drug timepoints. An unpaired Student's T-test will be used for the pairwise comparison if the data are normally distributed and a Mann-Whitney rank test will be used for nonparametric data. Normality will be assessed based on the Shapiro-Wilk test at the 5% level. If the unpaired Student's T-test was selected, the difference in means and its 95% confidence interval will be produced.

Each treatment group will also be tested using a one-way analysis of variance (ANOVA) to obtain a common variance followed by a Dunnett's post-test to separately compare each FDY-5301 dose group to placebo.

The same summarization method and statistical analyses will be repeated by baseline TIMI flow (grade 1 and lower, or, grade 2 and 3) and infarct type (anterior or other).

The changes from baseline in infarct size parameters may be compared between treatment groups in the form of a frequency table as necessary. The definition for these changes from baseline categories will be determined at a later stage based on the actual data.

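### MSI rests on one post-dose edema scan whose area at risk is never compared between arms, and the SAP's MSI test of change from 72 hours removes salvage already achieved by then

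*Protocol*

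**What the plan says.** Protocol section 10 makes edema imaging the source of AAR: "The primary estimate of AAR and hence MSI will be based on CMR imaging of myocardium for edema". It adds a second measure that does not depend on edema: "secondarily the length of coronary artery occluded will be document at the time of PCI". No analysis in either document uses that second measure.

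The sequences differ by visit. At the first scan: "The 72 hour CMR will include cine, T2W and LGE imaging for function, edema and necrosis respectively". At the second: "The 3 month CMR will include cine and LGE for function and late scar quantification respectively". Only the first scan images edema, and it falls 48 to 96 hours after dosing (Protocol 5.5.5 and Table 2).

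MSI is nevertheless listed at 3 months. Protocol 5.5.8 has "CMR to measure MSI, INF/VV, INF and cardiac function including EDV, ESV, FS and EF", and SAP 11.4.2.1 has "INF/VV, MSI, and INF will be assessed by CMR at 72 ± 24 hours post-study drug and 3 months post-study drug". Neither document says which AAR a 3-month MSI uses. SAP 11.4.2.1 takes the 72-hour scan as baseline, summarises observed values, and tests change from that baseline between pooled FDY-5301 and placebo. The ANOVA and Dunnett paragraph that follows names no other quantity. AAR is not among the parameters.

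Protocol 3.3 says that in preclinical work the drug "reduces neutrophil infiltration and down-regulates the inflammatory response in the reperfused myocardial tissue". It does not mention edema.

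**The concern.** MSI is the share of AAR that did not become infarct. It measures salvage only if treatment leaves AAR unchanged. Here AAR is read after dosing from a signal that an anti-inflammatory drug could plausibly lower. A smaller measured AAR in the active arms would lower their MSI and pull the between-arm difference toward zero. A flat MSI result could then mean either no salvage or reduced edema, and no planned AAR comparison would help to separate the two.

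The 3-month analysis raises a second, independent problem. If the 72-hour AAR is carried forward, subtracting 72-hour MSI from 3-month MSI cancels the benefit that a drug given before reperfusion is meant to produce.

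MSI is one of three outcomes for which the plan states power (Protocol 14.1.4, SAP section 9).

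**Working it through.** **Inputs.** From Protocol 14.1.4: 20 placebo and 60 pooled active patients, 80% power, a 24% increase in MSI with SD 20%, and a 37% reduction in INF/VV. Assumed: two-sided 5%, a t-test, and MSI = 1 − INF/AAR. The documents state no alpha, sidedness, control MSI or MSI formula.

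**The plan's own figure.** SE = 20 × √(1/20 + 1/60) = 5.16 points.
- If 24% means absolute points, 24/5.16 = 4.65 and power is 99.6%, not 80%.
- If 24% is relative, the difference detectable at 80% power is 14.65 points (noncentral t, 78 df). The implied placebo MSI is 14.65/0.24 = 61 points, or 0.61.
- At one-sided 5%, the same steps give 12.95 points and a placebo MSI of about 0.54.

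The stated 80% therefore fits a relative reading, but cannot be confirmed without the control value.

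**Consistency with the INF/VV figure.** At placebo MSI 0.61, INF/AAR = 0.39. A 37% smaller infarct with AAR unchanged gives MSI = 1 − 0.39 × 0.63 = 0.754, and 0.754/0.61 = 1.24. The two planning effects agree at 0.61 with AAR fixed. At 0.54 the result is 1 − 0.46 × 0.63 = 0.710, a 31.5% rise, so this agreement depends on the two-sided reading.

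**Effect of a smaller AAR on observed MSI.** With AAR lower by a fraction c in the active arms (assumed), active MSI = 1 − 0.39 × 0.63/(1 − c).

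| AAR reduction c | Active MSI | Gain (points) | Power, two-sided 5% |
|---|---|---|---|
| 0 | 0.754 | 14.4 | 79% |
| 10% | 0.727 | 11.7 | 61% |
| 20% | 0.693 | 8.3 | 35% |
| 30% | 0.649 | 3.9 | 12% |
| 37% | 0.610 | 0 | null |

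Cancellation is complete only when AAR falls by the same fraction as the infarct.

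**Range over placebo MSI.** Hold the true gain at 14.65 points and let AAR fall 20%. At placebo MSI 0.50 the observed gain is 1 − 0.3535/0.8 − 0.50 = 5.8 points (power 20%). At 0.70 it is 1 − 0.1535/0.8 − 0.70 = 10.8 points (power 54%).

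**What the SAP's change test measures.** With the 72-hour AAR reused:

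(1 − INF at 3 months/AAR) − (1 − INF at 72 h/AAR) = (INF at 72 h − INF at 3 months)/AAR.

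This is infarct shrinkage after 72 hours, scaled by AAR. As an illustration, assume infarcts in both arms shrink by the same fraction s after 72 hours and AAR is unaffected. The change is then 0.39s on placebo and 0.39 × 0.63 × s = 0.246s on active drug. The arm with more salvage shows the smaller improvement.

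**What an AAR comparison can show.** With 20 vs 60, 80% power is reached at (1.960 + 0.842) × √(1/20 + 1/60) = 0.72 SD.

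**The case against.** The strongest reply is that the power table describes a test the SAP does not run. That is correct. The table applies to observed MSI compared between arms, as Protocol sections 4.2, 11 and 14.1.6 envisage. Under the SAP's change test, a smaller AAR multiplies the active arm's change by 1/(1 − c), for example 1.25 at 20%, and so enlarges it. Attenuation is a problem for observed MSI; the change test has the separate fault of cancelling early salvage.

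The mechanism is also assumed. A reader might infer that the drug does reduce edema and that MSI is invalid. The documents do not support that: Protocol 3.3 speaks of neutrophils and inflammation, preclinically, and the 10% to 30% range is illustrative.

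A reader might also infer that real salvage would be hidden altogether. INF and INF/VV do not use AAR and are summarised beside MSI, and troponin AUC is compared too, so an infarct benefit could still appear. Each patient's AAR can be recovered as INF/(1 − MSI) where INF is above zero. This shows that reporting AAR is easy, but group summaries of INF and MSI do not give an AAR difference with an interval.

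A third tempting reading is that the 3-month scan makes MSI impossible. It cannot supply MSI alone, but the 72-hour AAR with the 3-month scar can; what is missing is the definition. Nor does the change test simply repeat the INF test: dividing by each patient's own AAR makes it a different quantity.

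Finally, Protocol section 10 says "Detailed instructions for the conduct and interpretation of the CMR will be available in a separate document, including the parameters to be analyzed". That document was not available and may define 3-month MSI. It would not replace a between-arm AAR comparison in the SAP. MSI is also a secondary, exploratory outcome, which limits the stakes.

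**Conclusion.** The point holds in two parts.

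First, neither the Protocol nor the SAP compares the post-dose edema AAR between arms or uses the occluded-artery length recorded at PCI, so an MSI result cannot be separated from a possible drug effect on edema. The consequence for observed MSI is attenuation, complete only if AAR falls as much as the infarct. At 20% it would take power from about 79% to about 35%, or anywhere from 20% to 54% over placebo MSI 0.50 to 0.70 at a fixed true gain. These figures rest on an assumed edema effect, two-sided 5%, the standard MSI formula and a back-solved placebo value.

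Second, and without any assumption about edema, a 3-month MSI that reuses the 72-hour AAR makes the SAP's MSI test one of infarct shrinkage after 72 hours. It does not test the salvage achieved by 72 hours. SAP section 13 does not list the move to change from 72 hours among its departures from the protocol.

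Both should be corrected before database lock. Neither affects INF or INF/VV through AAR.

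**What to change.** In SAP 11.4.2.1:

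1. Report 72-hour AAR by arm, with the overall FDY-5301 minus placebo difference and 95% CI, beside MSI. Read it as an estimate: with 80% power only at about 0.7 SD, a non-significant difference does not validate MSI.
2. Define 3-month MSI as (72-hour AAR − 3-month INF)/72-hour AAR, and state the same in Protocol 5.5.8.
3. Replace the MSI test of change from 72 hours with between-arm comparisons of observed MSI at 72 hours and at 3 months. Deleting the change test without this replacement would leave MSI with no test.
4. Optionally, add a supportive comparison of INF and INF/VV adjusted for the occluded-artery length recorded at PCI.

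Agree the definitions with the separate CMR document. The cost is SAP wording, one sentence in the protocol and one or two tables. AAR must already be derived to compute MSI, so no new scan is needed.

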11 STUDY OUTCOMES

Primary Outcome: The primary outcome for this study will be the combined number and incidence rate of several arrhythmias of interest that occur in each group over a 14 day period post-study drug.

These arrhythmias including ventricular fibrillation, sustained ventricular tachycardia (≥ 125 BPM, ≥ 30 seconds), non-sustained ventricular tachycardia (≥ 125 BPM, ≥ 16 beats, < 30 seconds) and high degree AV block (2nd or 3rd degree, ≥ 8 beats) were chosen because they are significant prognostic indicators of depressed left ventricular ejection fraction and cardiac death [1].

The combined number of arrhythmic events in each group will be calculated along with the arrhythmia incidence rate defined as the percentage of patients in each group experiencing at least one of the defined arrhythmias of interest.

An exploratory sub-analysis will be conducted to determine the number and incidence rate of each separate arrhythmia type per dose group.

Continuous ECG monitoring will occur from post reperfusion until 14 days post study drug by means of wearable ECG recorders. These will be positioned and activated as soon as feasible after treatment with study drug is complete.

Blinded, standardized centralized interpretation will be used for analysis of arrhythmias recorded with the wearable device.

Descriptions of peri-procedural arrhythmias such as reperfusion arrhythmias or VF episodes occurring prior to application of the wearable cardiac monitor will be categorized and documented separately on the CRF, with particular emphasis on persistent arrhythmias.

Secondary Outcomes:

- Infarct size parameters will be assessed by CMR at 72 +/- 24 hours and at 3 months; the following will be compared between groups; infarct size as a proportion of ventricular volume (INF/VV), myocardial salvage index (MSI) and absolute MI size
- The proportion of patients with ST-segment resolution at 4 hours post study drug
- Serum levels of troponin calculated as AUC 0-48 hours post-study drug

- Serum biomarkers of cardiac injury, inflammation and remodeling out to 3 months of follow up
- Persistent arrhythmias at 30 days and 3 months
- Measures of cardiac function by CMR including EDV, ESV, FS and EF
- Cardiac-related adverse events including the development of heart failure out to three months of follow up.

Incidence of all-cause and cardiac mortality out to 6 months of follow up

12 ASSESSMENT OF PHARMACOKINETICS, TROPONIN AND LABORATORY SAFETY MEASURES

12.1 Pharmacokinetics: Blood Iodide Levels

12.1.1 Pharmacokinetic Evaluation

The concentrations of FDY-5301 will be measured in plasma. 6 mL of blood should be collected in a lithium heparin tube. Every effort should be made to collect the PK samples as close to the time points listed below.

- Pre-study drug
- 2 minutes, 1, 4, 24 and 48 hours post-study drug

The pharmacokinetic analysis will include calculations of concentration-time profiles in subjects following dosing with study drug. Mean, standard deviation (SD) and CV will be calculated at each time point. For each dose group, the pharmacokinetic behavior of blood iodide will be described as area under the concentration versus time curve (AUC, AUC_{inf}) the maximal concentration (C_{max}), the time (T_{max}) when the maximal concentration is achieved, the apparent terminal elimination rate (K_{el}) and terminal half-life (T_{1/2}) for each subject. From this information, the total body clearance (CL), and the volume of distribution (V) will be derived.

12.2 General Safety

Safety and tolerability measurements will include:

- Physical examination
- Vital signs, including monitoring of blood pressure, pulse and heart rate
- Blood samples will be collected for hematology, clinical chemistry, coagulation parameters and thyroid function tests
- Adverse events

12.2.1 ECGs

12 lead ECGs will be used to confirm STEMI diagnosis during screening, document peri-procedural arrhythmias during treatment, obtain baseline ST-segment elevation prior to treatment and in order to evaluate ST segment resolution 4 hours post-study drug. In addition, 12 lead ECGs will be used to confirm any persistent arrhythmias at the following time points:

- 30 days post-study drug
- 3 months post-study drug

12.2.2 Biochemistry

Samples will be analyzed for sodium, potassium, chloride, bicarbonate, glucose, urea, urate, creatinine, phosphate, total and, albumin, total protein, total and conjugated bilirubin, GGT, alkaline phosphatase (ALP), alanine aminotransferase (ALT), aspartate transaminase (AST), lactate dehydrogenase (LD), TSH, T3 and free T4 at the time points listed below:

- Pre-study drug
- 4, 12, 24 and 48 hours post-study drug

12.2.3 Hematology

Samples will be analyzed for ACT (during anticoagulant administration only) hemoglobin, red blood cell count (RBC), packed cell volume (PCV), mean corpuscular volume (MCV), mean corpuscular hemoglobin (MCH), mean corpuscular hemoglobin concentration (MCHC), platelets, white cell count (WCC), and absolute counts of neutrophils, lymphocytes, monocytes, eosinophils and basophils at the time points listed below:

- Pre-study drug
- 4, 12, 24 and 48 hours post-study drug

12.2.4 Troponin Levels

In order to calculate AUC 0-48 hours, serum troponin T levels will be measured at the following time points:

- Pre-study-drug
- 12, 24, 48 hours post-study drug

12.2.5 Other Biomarkers of Cardiac Injury and Inflammation

Serum biomarkers of cardiac injury, inflammation and remodeling will be measured at the following time points:

- Pre-study drug
- 1,4,12, 24 and 48 hours post-study drug
- 3 months post-study drug

